## 2 Objectives and Estimands

### 2.1 Primary Objective

To determine the effects of pitavastatin on the morphology and composition of coronary atherosclerotic plaque, (including the progression of noncalcified plaque (NCP) volume), and whether these effects are modulated by markers of inflammation and immune activation.

Primary Estimand	
Estimand description	An estimand defines the target of estimation for a particular trial objective (i.e. “what is to be estimated”). This combines all the estimand elements outlined below into a single, succinct sentence.
Treatment	Treatment groups
Pitavastatin 4mg per day	Pitavastatin 4mg per day or placebo
Target population	Analysis set
PWH on stable ART with low to moderate cardiovascular risk and no known current indication for statin treatment.	All randomized participants with a REPRIEVE (A5332) entry visit. Participants who were consented but never returned to the clinic for their REPRIEVE (A5332) entry visit (regardless of whether the participant was formally randomized) will be considered inadvertent enrollments and excluded.
Variable(s)	Outcome measure(s)
Change in noncalcified plaque volume (NCP)  Change in volume of plaque and calcified plaque will be examined as secondary variables.	See Section 3 for more detailed outcome descriptions • Absolute change in NCP volume from entry to year 2. • NCP progression defined as any increase (>0) in NCP volume or incident NCP for those without NCP at entry (based on qualitative read) For sensitivity analyses, • Qualitative assessment of at least one segment with NCP on the 2 year CT. • Quantitative NCP volume at 2 year CT
Handling of intercurrent events	Handling of missing data

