##### 3.2.1 Change NCP volume over 2 years (Primary)

- Continuous outcome:
  - Absolute change: NCP volume at 2 years – NCP volume at entry
  - Percentage change: (NCP volume at 2 years – NCP volume at entry) / NCP volume at entry (Supportive)
- Based on quantitative read whenever available (including for participants with no evidence of NCP based on the corresponding qualitative read).
  - Participants without a quantitative read and no evidence of NCP based on the corresponding qualitative read will be assigned a value of zero for both absolute and percentage change.

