## 7 Analysis Plan

### 7.1 General analysis Considerations

Outcome distributions will be described with median, Q1, Q3, P10, P90, minimum, and maximum and shown graphically. All primary treatment group comparisons will be performed ITT using a 5% type error. For continuous outcomes, inference will be based on differences in means adjusted for baseline and presented with two-sided, 95% confidence intervals.

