#### Table: Primary and secondary plaque outcomes

Among participants with plaque at entry, descriptive statistics for the change and percentage change in NCP volume over 2 years will be provided by treatment group with group comparisons made with linear regression with adjustment for baseline plaque volume and stratified by sex and CD4.

Among those without NCP at entry, the prevalence of incident NCP over 2 years will be compared with stratified chi-squared test.

To assess the mechanistic study population as a whole, the probability of NCP and total plaque progression over two years (see Section 3.2.2) will be compared by treatment group using a stratified chi-squared test.

The statin effect on high risk plaque features (any), including low attenuation and positive remodeling, will be assessed by comparing differences in the 2-year prevalence of high risk plaque morphology features between treatment groups using chi-squared (or Fisher's exact) tests as appropriate; these analyses will be performed overall and by subgroups defined by the presence of NCP at study entry.

*Sample table from Testosterone study, JAMA 2017*

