## Appendix I Sample Size Considerations

[Copied Verbatim from the REPRIEVE A5333S Protocol, Version 5.0, Section 9.2.]

The target sample size for the Mechanistic Substudy of REPRIEVE (A5333s) is 800 participants that will be approximately equally distributed between the study arms.

This sample size was determined to have high power to detect clinically relevant differences between the two study groups both with respect to plaque progression (among those with plaque at study entry) and rates of incident plaque (among those plaque-free at entry). Specifically, the total sample size of 800 subjects will provide 90% power to detect a 6% difference between the study groups in the percent change in NCP volume over 2 years among those with plaque at entry and 90% power to detect 13 percentage point difference in the probability of plaque development over 2 years. These effect sizes translate to a combined estimated 14 percentage point difference in the probability of NCP progression over two years and are based on the following assumptions:

50% of study participants will have evidence of NCP at study entry [Lo 2010]

A SD of 20% for the percent change over 2 years among participants with evidence of plaque at entry

An annual rate of incident plaque development of 12% among participants without plaque at entry

15% of participants entering the substudy will not be evaluable for study entry or 2 year NCP volume.

Together, the effects of statins acting in these two groups (those with and without evidence of NCP at study entry) will provide for a 7% lower prevalence of NCP after 2-years of statin treatment. Expectations for NCP prevalence and progression both as a whole and according to whether NCP was present at study entry are illustrated in the table below. These estimates are based on a simulation that further assumed the following:

Average volume NCP 250mm^3 (SD=200) among participants with NCP at entry.

Average volume NCP 40mm^3 (SD=20) at 2 years among participants without NCP at entry without statin treatment.

Average volume NCP 20mm^3 (SD=20) at 2 years among participants without NCP at entry with statin treatment.

NCP distributions were also assumed to follow a gamma distribution with size and shape parameters determine to provide the desire mean and standard deviations.

Table 9.2-1: Cells constituting the primary targeted group comparisons are shown in bold.

		At study entry			At two 2 years						

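### The substudy's 90% power is for percent change in plaque volume, but the SAP's primary scale is mm3, on which the plaque-at-entry comparison has about 71–74% power and the all-paired-scan analysis about 90%

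*SAP*

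**What the plan says.** **Sizing.** SAP Appendix I is reproduced from Protocol Appendix II, section 9.2. It states that "the total sample size of 800 subjects will provide 90% power to detect a 6% difference between the study groups in the percent change" among those with plaque at entry. The target is "800 participants that will be approximately equally distributed between the study arms", half are assumed to have NCP at entry, and 15% are assumed not evaluable. The spread assumed is "A SD of 20% for the percent change over 2 years among participants with evidence of plaque at entry". Table 9.2-1 shows the percent-change cells for this group (12% vs 5%, SD 20% each) in bold as a targeted comparison. The same table also gives means and SDs for change in mm3.

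**Outcome.** Protocol Appendix II, 9.1.1.2, lists absolute and percent change together as a primary endpoint. The SAP narrows this. The outcome in the 2.1 estimand table is "Absolute change in NCP volume from entry to year 2", and 3.2.1 marks the percentage version, divided by "NCP volume at entry (Supportive"), as not primary. Binary NCP progression is a second primary outcome. The SAP version history does not mention the change of scale.

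**Analysis.** SAP 7.1 says "All primary treatment group comparisons will be performed ITT using a 5% type error" and that differences are "presented with two-sided, 95% confidence intervals". The 2.1 estimand and 4.1 define the set as all participants with an entry visit, with change analysed in those with paired scans. SAP 7.2 instead describes the comparison of change and percentage change among participants with plaque at entry, with "group comparisons made with linear regression with adjustment for baseline plaque volume and stratified by sex and CD4". Its only whole-population test is for binary progression.

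**The concern.** The only power figure for a continuous plaque outcome is on a scale that the SAP made supportive. There is no figure for absolute change, either in the plaque-at-entry group that 7.2 tests or in the full paired-scan set that 2.1 defines. The two scales do not have the same power. If percent change has a roughly constant SD, the SD of the change in mm3 grows with entry volume, so the largest plaques dominate the variance.

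A reader who carries the 90% over to the mm3 comparison in 7.2 would think the planned effect is missed about one time in ten, when the plan's own figures put it nearer three in ten. A null mm3 result in that group could then be given more weight than it deserves.

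**Working it through.** **Inputs.** Evaluable with plaque at entry: 800 × 0.85 × 0.50 = 340, so n = 170 per arm. All evaluable: 800 × 0.85 = 680, so 340 per arm. Two-sided 5%. Means and SDs come from Table 9.2-1.

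**Formula.** Power = Φ(d / √((s₁² + s₂²)/n) − 1.96).

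**1. The plan's own figure (percent change, SD 20%, n = 170).** The standard error is 20 × √(2/170) = 2.169.
- 6 points: 6/2.169 − 1.96 = 0.806, power 79.0%.
- 7 points (12% vs 5%): 7/2.169 − 1.96 = 1.267, power 89.7%.

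The 90% therefore reproduces at the table's difference and not at the one in the text. The comparisons below use the table's values throughout.

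**2. Absolute change, plaque at entry.** 30 (68) vs 12 (64), d = 18 mm3, n = 170.
- Standard error = √((4624 + 4096)/170) = 7.162.
- 18/7.162 − 1.96 = 0.553, power **71.0%**.
- With no losses (200 per arm): 77.8%.
- Difference detectable with 90% power: (1.960 + 1.282) × 7.162 = 23.2 mm3, against the planned 18.
- Evaluable participants needed for 18 mm3 at 90% power: 283 per arm.

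**3. Why adjusting for entry volume helps little.** Take entry volume B with mean 250 and SD 200, and percent change with SD 0.20 independent of B.
- E[B²] = 62,500 + 40,000 = 102,500.
- Control-arm variance of change = 0.20² × 102,500 + 0.12² × 40,000 = 4,100 + 576 = 4,676, so SD 68.4, which matches the table's 68.
- Linear adjustment can remove only the 576. The residual SD is about √4,100 = 64.
- With d = 18 and SD 64: 18/(64 × √(2/170)) − 1.96 = 0.633, power 73.7%.

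Two simulations used a gamma entry volume and the table's percent changes, so the implied difference is 250 × 0.07 = 17.5 mm3. They gave 70.7% and 71.8% adjusted, and 67.6% and 69.3% unadjusted. The adjusted range is thus 71–74%.

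**4. Absolute change, all paired scans.** 19 (51) vs 7 (45), d = 12 mm3, n = 340.
- Standard error = √((2601 + 2025)/340) = 3.689.
- 12/3.689 − 1.96 = 1.293, power **90.2%**.
- Simulated: 90.1% and 89.7% unadjusted, 92.1% and 92.3% adjusted.

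**5. Log scale, plaque at entry.** The same simulations, with a log-volume regression adjusted for log entry volume, gave 90.7% and 89.3%.

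| Comparison | n per arm | Power |
|---|---|---|
| Percent change, plaque at entry, 6 points | 170 | 79.0% |
| Percent change, plaque at entry, 7 points | 170 | 89.7% |
| mm3, plaque at entry, unadjusted | 170 | 71.0% |
| mm3, plaque at entry, adjusted | 170 | 71–74% |
| Log volume, plaque at entry, adjusted | 170 | 89–91% |
| mm3, all paired scans, unadjusted | 340 | 90.2% |
| mm3, all paired scans, adjusted | 340 | about 92% |

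**The case against.** The best defence has four parts.

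- **The estimand set is adequately powered.** The set in SAP 2.1 is everyone with an entry visit and paired scans, and 3.2.1 assigns zero change to participants with no quantitative read and no NCP. Plaque-free people are therefore in the outcome, and power there is about 90%. This stands, and it limits the point to the plaque-at-entry comparison.
- **Appendix I does not claim 90% for mm3.** It says the figure is for percent change, and 7.2 still compares percent change in the same participants. This also stands. What is missing is a figure for the scale that the SAP made primary.
- **There is a log fallback.** SAP 2.1 allows log transformation, with a percentage interpretation, if normality is extremely violated. Under the plan's gamma model this is plausible: simulated residuals of the adjusted mm3 regression had a median excess kurtosis of about 6. If it is used, power returns to about 90%. But no criterion for extreme violation is given, so it cannot be counted on.
- **Nothing can be re-sized.** Substudy enrollment closed in February 2018 and the SAP was finalized in March 2023. Confidence intervals will show the precision achieved. That is true, and it is why the remedy is confined to wording and labelling.

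**Conclusion.** The mismatch is real but bounded. On the SAP's primary scale, the plaque-at-entry comparison in 7.2 has about 71% power unadjusted and 71–74% adjusted for the planned 18 mm3 difference, against 89.7% for the corresponding 7-point percent change. On those table values the chance of missing the effect is about 26–29% rather than 10%. Against the 6% written in the text, the percent-change figure is itself 79.0%, a miss rate of about 21%.

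A reader might infer that the substudy's primary continuous analysis has only 71% power. The documents do not support that: for the set named in 2.1 and 4.1, the same table gives 90.2% unadjusted and about 92% adjusted. A reader might also infer that mm3 is the wrong scale. That is not supported either. The protocol listed both scales, the estimand's summary measure is mean change in volume, and choosing mm3 is legitimate. What does need resolving is that 2.1 and 4.1 point to one population for the continuous comparison and 7.2 to another, with no power stated for mm3 in either.

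These figures rest on the planning assumptions in Appendix I (50% with plaque, 15% not evaluable, the table's means and SDs), a normal approximation for the unadjusted results, and percent change independent of entry volume for the adjusted ones. The all-participant figure also follows the table in giving zero change to people who have no plaque at either scan.

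**What to change.** 1. **SAP Appendix I.** Add a short note after the copied text. For absolute NCP change, power is about 71–74% among participants with plaque at entry (18 mm3, 170 per arm) and about 90–92% in all paired scans (12 mm3, 340 per arm). State that the 90% for percent change holds at the table's 7-point difference (89.7%) and not at 6% (79.0%).
2. **SAP 2.1, 4.1 and 7.2.** Reconcile the population. Name the baseline-adjusted regression in all participants with paired scans as the primary continuous test, and label the plaque-at-entry mm3 comparison a lower-powered subgroup analysis.
3. **Optional.** In the plaque-at-entry group, add a regression of log year-2 volume on treatment, log entry volume, sex and CD4, labelled supportive (about 90% power under the plan's model). It should not replace the mm3 estimand.

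**Cost.** Items 1 and 2 are wording only and need no new data, but a less favourable power figure goes on record. Item 3 is one extra regression; its result is a ratio rather than mm3, and any zero volume would need an offset. Because version 1.1 of the SAP was prepared for public release, these changes should appear as a dated, labelled addition.
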